9.8.2. Azacitidine Dose Modifications and Stopping Criteria

The first treatment cycle of azacitidine should always be given at 100% of the dose, regardless of a subject's laboratory values (provided that the subject is allowed to enroll in the study based on the inclusion and exclusion criteria).

Subjects should be monitored for hematologic toxicity and renal toxicity; a delay in starting the next azacitidine treatment cycle or an azacitidine dose reduction, as described below, may be necessary. If the dose of azacitidine is modified during the course of the study (see below) and benefit is demonstrated at the reduced dose, that dose should be maintained during subsequent cycles (unless toxicity develops). The Investigator should contact the Medical Monitor for guidance on azacitidine dose modification, if needed.

The initiation of a new cycle will start 21 days after administration of the Day 7 (± 3 days) dose of azacitidine if administered over 7 continuous days or 19 days after the Day 9 (± 3 days) dose if administered on a 5-2-2 schedule. The initiation of a new cycle will start upon the ability to reinitiate combination therapy.

If azacitidine is permanently discontinued for non-hematologic or hematologic toxicities, AG-120/placebo may continue at the discretion of the Investigator and with agreement from the Medical Monitor, provided that the subject is in CR or CRi (including CRp) and needs to discontinue azacitidine due to protocol-specified azacitidine-related toxicity (eg, delayed bone marrow recovery).

9.8.2.1. Azacitidine Dose Modifications due to Non-Hematologic Toxicity

Following receipt of any dose of azacitidine, subsequent treatment cycles may be delayed if a certain level of toxicity occurs after the previous dose. Any subject who experiences a non-hematologic AE of Grade 3 or 4 that is thought to be causally related and is an escalation from his or her status at baseline should have azacitidine temporarily discontinued until the toxicity grade returns to Grade <3 . Azacitidine should be permanently discontinued if the non-hematologic toxicity persists as Grade 3 or 4 for more than 3 weeks (21 days), despite the temporary interruption of azacitidine.

9.8.2.2. Azacitidine Dose Modifications due to Hematologic Toxicity

Treatment with azacitidine is associated with anemia, neutropenia, and thrombocytopenia, particularly during the first 2 cycles. Complete blood counts should be performed as specified in the Schedule of Assessments (Table 6), and as needed to monitor toxicity.

Recovery is defined as an increase of cell line(s) where hematologic toxicity was observed of at least half of the difference of nadir and the baseline count plus the nadir count (ie, blood count at recovery \geq Nadir Count + $(0.5 \times [\text{Baseline count} - \text{Nadir count}]$).

For example, if the baseline, pre-cycle neutrophil count is $500 \times 10^9/\text{L}$ and the Nadir count is $100 \times 10^9/\text{L}$, recovery is defined as: $\geq 100 + (0.5 [500 - 100])$, $\geq 300 \times 10^9/\text{L}$.

Subjects without reduced baseline blood counts (ie, WBC count $>3.0 \times 10^9/\text{L}$, ANC $>1.5 \times 10^9/\text{L}$, and platelets $>75.0 \times 10^9/\text{L}$) prior to first treatment:

If hematologic toxicity is observed following azacitidine treatment, the next cycle of azacitidine therapy should be delayed until the platelet count and the ANC have recovered. If recovery is achieved within 2 weeks (14 days), no dose adjustment is necessary. However, if recovery has not been achieved within 2 weeks, the azacitidine dose should be reduced according to Table 2. Following dose modifications, the cycle duration should return to 4 weeks (28 days). The reduced dose should be maintained during subsequent cycles that are given (unless toxicity develops). A flow diagram for the determination of azacitidine dose adjustment in subjects without reduced baseline blood counts is provided in Appendix 15.4.

Table 2: Hematologic Dose Reductions for Azacitidine Based on Absolute Neutrophil Count and Platelets

Nadir Counts		% Dose in the next course if recovery ^a is not achieved in next 2 weeks (14 days)
ANC ($\times 10^9/L$)	Platelets ($\times 10^9/L$)	
≤ 1.0	≤ 50	50%
> 1.0	> 50	100%

Abbreviations: ANC = absolute neutrophil count.

^a Recovery = counts \geq nadir count + $(0.5 \times [\text{baseline count} - \text{nadir count}])$.

Subjects with reduced baseline blood counts (ie, WBC count $\leq 3.0 \times 10^9/L$ or ANC $\leq 1.5 \times 10^9/L$ or platelets $\leq 75.0 \times 10^9/L$) prior to treatment:

Following azacitidine treatment, if the decrease in WBCs, ANC, or platelets from the value prior to treatment is less than 50%, or greater than 50% but with an improvement in any cell line differentiation, the next cycle should not be delayed and no dose adjustment made.

If the decrease in WBC count, ANC, or platelets is greater than 50% from the value prior to treatment, with no improvement in cell line differentiation, the next cycle of azacitidine therapy should be delayed until the platelet count and the ANC have recovered. If recovery is achieved within 2 weeks, no dose adjustment is necessary. However, if recovery has not been achieved within 2 weeks, bone marrow cellularity should be determined. If the bone marrow cellularity is $>50\%$, no dose adjustments should be made. If bone marrow cellularity is $\leq 50\%$, azacitidine treatment should be delayed and the dose reduced according to [Table 3](#).

Table 3: Hematologic Dose Reductions for Azacitidine Based on Bone Marrow Cellularity

Bone Marrow Cellularity	% Dose in the next course if recovery ^a is not achieved in next 2 weeks (14 days)	
	Recovery ≤ 3 weeks	Recovery > 3 weeks
15% to 50%	100%	50%
$< 15\%$	100%	33%

^a Recovery = counts \geq nadir count + $(0.5 \times [\text{baseline count} - \text{nadir count}])$.

Following azacitidine dose modifications, the cycle duration should return to 4 weeks (28 days). The reduced dose should be maintained during subsequent cycles that are given (unless toxicity develops). A flow diagram for the determination of azacitidine dose adjustment in subjects with reduced baseline blood counts is provided in [Appendix 15.4](#).

9.8.2.3. Azacitidine Therapy and Renal Dysfunction

Renal abnormalities ranging from elevated serum creatinine to renal failure and death were reported rarely in subjects treated with IV azacitidine in combination with other chemotherapeutic agents. In addition, renal tubular acidosis, defined as a fall in serum bicarbonate to <20 mmol/L in association with an alkaline urine and hypokalemia (serum potassium <3 mmol/L) developed in 5 subjects with chronic myelogenous leukemia treated with azacitidine and etoposide. If unexplained reductions in serum bicarbonate (< 20 mmol/L) occur, the dose should be reduced by 50% on the next course. Similarly, if unexplained elevations in

serum creatinine or blood urea nitrogen (BUN) to ≥ 2 -fold above baseline values and above ULN occur, the next cycle should be delayed until values return to normal or baseline and the dose should be reduced by 50% on the next treatment cycle. The reduced dose of azacitidine should be maintained during subsequent cycles that are given (unless toxicity develops).

The main excretion route of azacitidine is through the urine; additional caution is warranted if renal impairment is present at baseline.

AG-120/placebo should continue to be taken if azacitidine is interrupted beyond the 4-week (28-day) cycle as long as daily AG-120/placebo dosing is not believed, in the opinion of the Investigator, to have been part of the reason for interruption.

9.9. Adverse Events of Special Interest for AG-120

The following are guidelines for the management of AESIs based on the nonclinical and clinical safety findings for AG-120.

9.9.1. QT Prolongation

The discussion of the emergency management of Torsades de pointes and its hemodynamic consequences is beyond the scope of this guideline.

Prolongation of heart-rate corrected QT interval using Bazett's method has been observed in monkeys at relatively high doses of AG-120 and has been identified as an expected risk of treatment with AG-120 (see the IB). Events of QT prolongation (ie, QTcF Grade ≥ 3) should be reported as AESIs to the Sponsor within 24 hours, according to expedited reporting procedures (see Section 11.2.3).

Subjects may be at increased risk for the development of QT prolongation when treated with AG-120 in combination with fluoroquinolones, azole antifungal agents, or serotonin (5-HT₃) antagonists. Investigators must be vigilant; refrain from administering concomitant medications associated with QT prolongation and if no other therapeutic options are available, monitor subjects receiving study treatment with the combination of these drugs and evaluate ECG and electrolytes (including potassium, magnesium, and calcium), particularly in subjects presenting with nausea, vomiting, or diarrhea. Systemic administration of a moderate or strong CYP3A4 inhibitor requires careful monitoring of QTcF.

Subjects who experience QT prolongation (ie, QTcF > 480 msec; NCI CTCAE Grade ≥ 2) while receiving study treatment should be promptly evaluated for causality of the QT prolongation and managed according to the following guidelines and Table 4:

- Levels of electrolytes (potassium, calcium, and magnesium) should be checked and supplementation given to correct any values outside the normal range.
- Concomitant therapies should be reviewed and adjusted as appropriate for medications with known QT prolonging effects.
- If no other cause is identified and the Investigator believes it is appropriate, particularly if QTcF remains elevated (after the above measures have been implemented, or as determined by the Investigator), study treatment may be interrupted, and an ECG should be rechecked in approximately 1 week after the QT prolongation event was first observed or more frequently as clinically indicated. If

QTcF has recovered or improved and the Investigator believes it is safe to do so, re-challenge with study treatment should be considered if held. Dose adjustments or interruptions for QTcF prolongation in the context of a pre-existing bundle branch block should be discussed with the Medical Monitor. Recommendations may deviate from Table 4 depending on the clinical context and the adjusted QTcF value. Consultation with a cardiologist is recommended in these circumstances.

- ECGs should be conducted at least weekly (eg, at every scheduled visit) for 2 weeks following QTcF reduction to ≤ 480 msec.

Table 4: Management of QT Prolongation by NCI CTCAE Grade

NCI CTCAE Grade	Management
Grade 2 (QTcF >480 and ≤ 500 msec)	
 • The dose of study treatment may be reduced to 250 mg QD without interruption of dosing. The dose of study treatment may be re-escalated to the prior dose in ≥ 2 weeks (14 days) after QT prolongation has decreased to \leq Grade 1.
Grade 3 (QTcF >500 msec on at least 2 separate ECGs)	
 • Hospitalization for continuous cardiac monitoring and evaluation by a cardiologist should both be considered. • Monitor electrolyte levels and supplement with electrolytes as clinically indicated. • Review and adjust concomitant medications with known QT prolongation effects. • Dosing with study treatment will be interrupted. If QTcF returns to within 30 msec of baseline or <470 msec within 2 weeks, treatment may be resumed at a reduced dose of 250 mg QD. • The dose of study treatment cannot be re-escalated following dose reduction for Grade 3 QT prolongation unless the prolongation was associated with an electrolyte abnormality or concomitant medication.
Grade 4 (QTcF >500 msec or >60 msec change from baseline with Torsades de pointes or polymorphic ventricular tachycardia or signs/symptoms of serious arrhythmia)	
 • Subjects should be admitted to a hospital for continuous cardiac monitoring and discharged only after review by a cardiologist. • Dosing with study treatment should be permanently discontinued.

Abbreviations: NCI CTCAE = National Cancer Institute Common Terminology Criteria for Adverse Events; QD = once daily; QTcF = heart-rate corrected QT interval using Fridericia's method.

Note: Per NCI CTCAE, version 4.03.

9.9.2. IDH Differentiation Syndrome

Events of IDH differentiation syndrome have been reported in subjects with hematologic malignancies in Study AG120-C-001 during treatment with AG-120 (see the IB). Any event of differentiation syndrome assessed as Grade ≥ 2 , irrespective of seriousness, should be reported to the Sponsor as an AESI within 24 hours (see Section 11.2.3).

Subjects treated with AG-120 have developed signs and symptoms of differentiation syndrome. Clinical features may include some or all of the following: unexplained fever, skin rash, hypoxia, respiratory compromise, interstitial pulmonary infiltrates, pleural and/or pericardial effusion,

weight gain, and clinical deterioration. Laboratory features may include an increase in ANC and/or platelets. An increase in mature leukocytes may be observed in the bone marrow aspirate differential if a bone marrow biopsy is conducted during this time. However, no single sign or symptom may be considered per se as diagnostic of the syndrome, and other causes should be sought and excluded. If IDH Differentiation Syndrome is suspected, and is Grade ≥ 2 , Investigators must report the suspected diagnosis as the AE: IDH Differentiation Syndrome.

Any event of IDH Differentiation Syndrome assessed as Grade ≥ 2 should be reported to the Sponsor as either an SAE or AESI depending on the clinical assessment of seriousness.

It is recommended that the prophylactic and therapeutic measures indicated below be undertaken at the earliest manifestations of suspected IDH differentiation syndrome:

- Temporary hold of AG-120/placebo if clinical features cannot be medically managed with the following:
 - Control of leukocytosis with hydroxyurea (see Section 9.13.4.3)
 - Prompt administration of corticosteroids at a suggested dose of 10 mg of dexamethasone IV every 12 hours until disappearance of symptoms and signs, and for a minimum of 3 days
 - Initiation of furosemide, if clinically required
 - Prompt initiation of leukapheresis, if required

Immediate communication with the Medical Monitor is encouraged for guidance regarding treatment. Once the signs and symptoms resolve and the subject's clinical condition improves, AG-120/placebo may be reinitiated if study treatment was held. The dose of AG-120/placebo at reinitiation is to be discussed with the Medical Monitor.

9.9.3. Leukocytosis

Events of leukocytosis have been reported in subjects with hematologic malignancies in Study AG120-C-001 during treatment with AG-120 (see the IB). Any event of leukocytosis assessed as Grade ≥ 3 , irrespective of seriousness, should be reported to the Sponsor as an AESI within 24 hours (see Section 11.2.3).

See Section 9.13.4 for guidance on the use of hydroxyurea in the event of leukocytosis.

The following guidelines must be used when grading the AE of leukocytosis:

NCI CTCAE Grade	Absolute Neutrophil Count/Clinical Manifestation Hydroxyurea Regimen
Grade 3	> 100,000/mm ³
Grade 4	Clinical manifestations of leukostasis; urgent intervention indicated
Grade 5	Death

Note: Per National Cancer Institute (NCI) Common Terminology for Adverse Events Criteria (CTCAE), version 4.03.

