9.10.3. Tumor Lysis Syndrome

Tumor lysis syndrome (TLS) is a potential risk associated with AG-120 treatment based on clinical safety findings in subjects with hematologic malignancies. Refer to the AG-120 IB for further details on events of TLS.

Tumor lysis syndrome was observed in 19 (7.4%) subjects with advanced hematologic malignancies in Study AG120-C-001, 2 (3.3%) subjects with newly diagnosed AML in Study AG120-221-C-001, and 1 (4.3%) subject with newly diagnosed AML in Study AG-221-AML-005. No events of TLS have been reported in Study AG120-C-009, Studies AG120-C-002 and AG120-C-005 in solid tumors, or in clinical pharmacology studies.

Development of TLS is a known risk associated with AML. Clinical risk factors include leukocytosis (with or without disease progression) and concurrent use of cytoreductive agents, such as hydroxyurea. AG-120 can induce myeloid proliferation resulting in a rapid reduction in tumor cells, which may pose a risk for tumor lysis syndrome. In some instances, TLS events occurred in subjects who also had rising WBC counts, suggesting the possibility that these events were related to the underlying malignancy or were co-occurring with IDH differentiation syndrome. Prophylactic and treatment measures for TLS should be employed as clinically indicated.

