9.13.4.3. Leukocytosis Prophylactics and Therapeutics (Hydroxyurea)

It is recommended that the prophylactic and therapeutic measures indicated below are undertaken at the earliest manifestations of leukocytosis:

- Temporary hold of study treatment only if symptoms cannot be medically managed with the following:
 - Prompt initiation of hydroxyurea at up to a dose of 2000 or 3000 mg PO BID
 - Prompt initiation of leukapheresis, if required

Treatment with hydroxyurea is allowed during treatment with AG-120/placebo + azacitidine for control of peripheral leukemic blasts in subjects with leukocytosis (WBC >30,000/ μ L).

Treatment with hydroxyurea prior to randomization is allowed (Table 5).

Immediate communication with the Medical Monitor during active management of leukocytosis is required. Once the signs and symptoms resolve and the subject's clinical condition improves, AG-120/placebo may be reinitiated if study treatment was held. The dose of AG-120/placebo at reinitiation is to be discussed with the Medical Monitor.

Table 5: Recommended Initial Doses of Hydroxyurea for Management of Leukocytosis

Hydroxyurea Dose and Regimen	Total White Blood Cell Count (μ L)	Absolute Increase in Total White Blood Cell Count from Baseline (μ L)
1000 mg QD	25,000 to 50,000	15,000 to 29,000
2000 mg BID	51,000 to 75,000	30,000 to 49,000
3000 mg BID	\geq 76,000	\geq 50,000

Abbreviations: QD = once daily, BID = twice daily.

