11.2.3.2. Leukocytosis

Any event of leukocytosis assessed as Grade ≥ 3 , irrespective of seriousness, should be reported to the Sponsor as an AESI within 24 hours.

See Section 9.13.4.3 for further details on managing subjects with leukocytosis.

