11.2.7. Progression of AML

Progression of AML (see Table 11) should not be reported as an AE if it is clearly consistent with the suspected progression of the underlying cancer. Clinical symptoms of progression may be reported as AEs if the symptoms cannot be determined as exclusively due to the progression of the subject's underlying AML or does not fit the expected pattern of progression for the disease.

If there is any uncertainty about an AE being due only to the disease under study, it should be reported as an AE or SAE.

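### The mandatory leukocytosis grading table labels its Grade 3 count as neutrophils, while the protocol manages leukocytosis by total white cells, so a few non-serious events could be under-graded

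*Protocol*

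**What the plan says.** Protocol Section 9.9.3 introduces its grading table with "The following guidelines must be used when grading the AE of leukocytosis". The column of criteria is headed "Absolute Neutrophil Count/Clinical Manifestation Hydroxyurea Regimen". Grade 3 is a count above 100,000/mm³, Grade 4 is clinical leukostasis and Grade 5 is death. The Grade 3 row names no cell type, so the heading is the only label for the count. A note beneath reads "Per National Cancer Institute (NCI) Common Terminology for Adverse Events Criteria (CTCAE), version 4.03".

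Section 9.13.4.3 works with a different count. It allows hydroxyurea during treatment at WBC above 30,000/µL, and Table 5 sets initial doses by total WBC and by "Absolute Increase in Total White Blood Cell Count from Baseline". It adds: "Immediate communication with the Medical Monitor during active management of leukocytosis is required".

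Section 11.2.3.2 says that leukocytosis of Grade 3 or higher, serious or not, "should be reported to the Sponsor as an AESI within 24 hours". It names no count.

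Sections 10.6.6 and 11.2 grade all adverse events by CTCAE 4.03, and Appendix 15.9 gives a link to it. The CTCAE text itself is not in the documents.

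**The concern.** A compulsory safety table and the management section of the same protocol use different measurements for the same event. Protocol Section 10.6.5 lists WBC with differential, the absolute neutrophil count (ANC) and the peripheral blast count separately, so the two labels are not interchangeable.

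The AESI rule matters most for non-serious events, because serious events already have a 24-hour route under Section 11.2. Non-serious events are also the ones that a neutrophil reading could drop. For QT prolongation, Section 11.2.3.1 repeats the numerical criterion beside the reporting rule, so an error elsewhere would be caught. The leukocytosis rule has no such repetition.

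At stake are the Investigator's grade, the formal 24-hour AESI report, and the tables of Grade 3 or higher events that use that grade (Protocol Section 12.6.1; SAP Sections 7.8.1 and 7.8.1.1).

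**Working it through.** The plan states no figure to reproduce. The check compares the text and then works out where the two readings differ.

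**Inputs**
- Grade 3 threshold: more than 100,000/mm³ (Protocol 9.9.3).
- Peripheral-blast criterion for progression: an increase of more than 50% to above 25,000/µL, without treatment-related differentiation syndrome (Protocol Table 11).
- Neutrophils are one component of the WBC differential (SAP 7.8.3.1).
- 1 mm³ equals 1 µL.
- The WBC values below are examples. No neutrophil share is assumed.

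**Step 1: direction.** ANC = WBC × neutrophil share, so ANC cannot exceed WBC. The printed heading can lower a grade but never raise it.

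**Step 2: where the readings differ.** They differ when WBC is above 100,000 and the neutrophil share is at or below 100,000/WBC.

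**Step 3: events likely to be progression.** Blasts exceed 25,000/µL once their share passes 25,000/WBC. Many such events will count as progression, which is not reported as an adverse event (Protocol 11.1.1, 11.2.7).

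**Step 4: what is left.** If ANC is at most 100,000 and blasts at most 25,000, the remaining white cells must number at least WBC − 125,000, or zero if that is negative.

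| WBC (/mm³) | Neutrophil share at or below which readings differ | Blast share above which blasts exceed 25,000 | Other white cells needed |
|---|---|---|---|
| 110,000 | 100/110 = 90.9% | 25/110 = 22.7% | 0 |
| 125,000 | 100/125 = 80.0% | 25/125 = 20.0% | 0 |
| 150,000 | 100/150 = 66.7% | 25/150 = 16.7% | 25,000 |
| 200,000 | 100/200 = 50.0% | 25/200 = 12.5% | 75,000 |

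Up to WBC 125,000, an event can therefore fall between the two readings without meeting the blast criterion and without any other cell type. Above that, it needs other white cells or a high baseline blast count. With an assumed baseline of 50,000/µL, blasts up to 50,000 × 1.5 = 75,000/µL are not a rise of more than 50%. WBC 150,000 made up of 75,000 blasts and 75,000 neutrophils then meets neither the blast criterion nor ANC above 100,000.

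**Step 5: whether such events would be reported as adverse events.** Section 9.10.3 on tumor lysis syndrome recognises leukocytosis that is not progression: "Clinical risk factors include leukocytosis (with or without disease progression" or without it. Section 11.2.7 sends unclear cases to adverse event reporting: "If there is any uncertainty about an AE being due only to the disease under study", the event is to be reported. So the group can exist. It is narrow, because relapse in Table 10 includes blasts reappearing in the blood, and differentiation syndrome of Grade 2 or higher is an AESI in its own right (Section 11.2.3.3).

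**Step 6: what such an event loses and keeps.** On the printed heading it is not Grade 3, so it misses the formal AESI trigger and the Grade 3 or higher tables. It stays in the all-grade AESI summaries, because SAP Section 7.8.1.1 finds leukocytosis events by search criteria and tabulates them at every grade.

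**The case against.** The strongest reply is that the table presents itself as a copy of CTCAE, not as a trial-specific rule. Its rows are labelled as CTCAE grades, its note cites version 4.03, and Sections 10.6.6 and 11.2 and Appendix 15.9 all point there. An Investigator who consults CTCAE may never use the heading. The heading is also visibly garbled, since the reference to a hydroxyurea regimen fits none of the rows. This stands as far as it goes: the slip is probably editorial, and the table is not the only grading instruction. But the table is compulsory and names one count, and without the CTCAE text one cannot say how far the note corrects it. The result is a conflict between instructions.

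The safeguards also carry weight. Serious events reach the Sponsor within 24 hours. Leukostasis is Grade 4 whatever the count. The Medical Monitor must be contacted during active management, and Table 5 recommends hydroxyurea from WBC 25,000. SAP Section 7.8.3 derives laboratory grades, where applicable, from CTCAE numerical thresholds and not from this table. The data monitoring committee sees relevant laboratory data (Section 10.6.1). In the single-agent study AG120-C-001, leukocytosis was an adverse event in 21% of subjects and a serious one in 9%. About 9/21 = 43% of those affected thus had a serious event, using rounded figures from a different population. These points reduce the harm. None of them corrects the Investigator's grade or supplies the missing AESI report.

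A reader might infer that the AESI trigger rests on this heading alone, that affected events vanish from safety reporting, or that ANC was chosen by design. The documents support none of these: grading is also referred to CTCAE 4.03, the all-grade summaries keep the events, and nothing in the protocol argues for a neutrophil criterion.

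**Conclusion.** The heading is wrong as written within this protocol: a compulsory safety threshold names a count that the protocol's own management of leukocytosis does not use. It is an internal inconsistency of minor severity.

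The consequence is possible under-grading of a small group: non-serious leukocytosis with WBC above 100,000/mm³, ANC at or below 100,000/mm³ and no leukostasis, not attributed to progression, relapse or differentiation syndrome. The loss is limited to the 24-hour AESI report and the tables of Grade 3 or higher events. Efficacy is not touched.

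Two limits apply. The frequency cannot be estimated from the documents, and the worked values show only that such events are possible. That total WBC is the intended count is inferred from Section 9.13.4.3 and Table 5, and needs confirming against CTCAE 4.03.

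**What to change.** After checking CTCAE 4.03, change the column heading in Section 9.9.3 to *Total White Blood Cell Count/Clinical Manifestation*, remove the words on the hydroxyurea regimen, and notify sites.

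Before database lock, query every on-treatment WBC above 100,000/mm³ that has neither a leukocytosis adverse event of Grade 3 or higher nor documented progression, relapse or differentiation syndrome. This also covers events graded before the heading is corrected.

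The cost is one heading, one site notice and one reconciliation query. WBC is already collected, and by-subject laboratory listings are already planned (Protocol Section 12.6.2; SAP Section 7.8.3).
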